9.2.3. Sample Size Sensitivity

No analysis of sample size sensitivity was performed.

9.2.4. Sample Size Re-estimation or Adjustment

Sample size re-estimation is not planned for this study.

9.3. Analysis Populations

The **All-Treated Population** is defined as all participants who receive at least one dose of GSK3368715.

All Evaluable Population is defined as the study population used for decision-making at the interim futility analysis. Participants who have had Week 24 disease assessments, have progressed or died, or permanently discontinued from the study intervention will be included in this population.

The **PK Population** will consist of all participants from the All-Treated Population for whom a PK sample is obtained and analyzed.

Additional analysis populations may be defined in the Reporting and Analysis Plan (RAP).

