4.1.2. Part 2: Expansion Cohorts

Part 2 (Dose Expansion) will start after the RP2D is determined in Part 1.

The intention of Part 2 is to (i) collect additional information on the safety and PK/PD characteristics of GSK3368715 and (ii) to evaluate the clinical activity of GSK3368715 in selected disease populations.

Part 2 will consist of two expansion cohorts:

- **Expansion Cohort 2A:** Up to 36 participants with DLBCL will be enrolled. Based on the assumed prevalence of MTAP deletions, it is expected that ~ 23 % of participants (or ~ 8 out of 36 participants) will present with DLBL deficient of MTAP.

For DLBCL cohort (Part 2A), this cohort will be evaluated separately from the solid tumor cohorts (Part 2B). A Bayesian adaptive design based on hierarchical model will be used to allow interim monitoring of the response rate and allow information borrowing between the MTAP defined subgroups within the cohort. The interim futility analysis will be performed every 2-3 months with minimum of 5 additional evaluable participants from the entire cohort. The first interim futility analysis will be performed when at least 5 participants become evaluable from each of the MTAP defined subgroups. Data from both subgroups will be included in the analysis to form the Bayesian hierarchical model. Any subgroup with posterior probability of ORR > 10% sufficiently low (<20%) will be declared as ineffective and terminated for enrollment according to the design.

- **Expansion Cohort 2B:** Up to 105 participants with pancreas cancer, NSCLC, and bladder cancer, will be enrolled. The number of participants with a specific tumor histology in this cohort will is not fixed but will ultimately not exceed 35 participants of any specific tumor histology.

The three tumor histologies were selected on the basis of the higher frequency of MTAP deletions which is assumed to be ~ 30% in pancreatic cancer, ~27-32% in bladder cancer, and ~9-28% in NSCLC.

A Bayesian adaptive design based on hierarchical model will be used to allow interim monitoring of the response rate in this expansion cohort on ongoing basis. The design will also allow information borrowing across the three different histologies as well as between the MTAP defined subgroups within each histology. Participants enrolled in Part 1 who were treated at the RP2D of GSK3368715 and have the same disease histology as required for Expansion Cohort 2B will be included in the analyses as appropriate.

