9.1.2. Dose Expansion

The primary goal of Part 2 is to evaluate clinical activity in each disease specific cohort for GSK3368715 for MTAP- subgroup and MTAP+ subgroup separately.

All evaluations in Part 2 are designed to exclude a 10% response rate representing best available therapy in favour of a 30% response rate.

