9.2.2. Dose Expansion

Part 2A DLBCL Cohort

ORR will be analyzed using a Bayesian hierarchical model that allows information borrowing between MTAP proficient and MTAP deficient subgroups within the DLBCL cohort. An MTAP defined subgroup will be considered as effective at the end of study if the posterior probability of ORR>10% is more than 85%. In this design, up to 30 participants will be enrolled into each MTAP defined subgroup and up to 36 will be

enrolled for the entire cohort. The simulation results assuming 50:50 ratio between MTAP proficient participants and MTAP deficient participants are displayed in [Table 9](#).

Assume $\pi_g = \Pr(\text{response} \mid \text{intervention, group } g)$ denote the probability of response for group g participants, where group g represents MTAP proficient subgroup or MTAP deficient subgroup, and $\pi = \Pr(\text{response} \mid \text{intervention})$ denote the probability of response for the entire cohort. Let $\theta_g + R_g$ be the logit of the group g response rate, $\theta_{AG} + R_g$ be the logit of the cohort response rate, i.e.,

$$\theta_g + R_g = \log\left(\frac{\pi_g}{1 - \pi_g}\right).$$

and

$$\theta_{AG} + R_g = \log\left(\frac{\pi}{1 - \pi}\right).$$

The hierarchical model assumes

$$\theta_g \sim N(\mu, \tau^2),$$

The prior distributions for μ , τ^2 and θ_{AG} are defined as follows:

$$\begin{aligned}\mu &\sim N(-2.2, 6.9), \\ \tau^2 &\sim IG(1, 47.61), \\ \theta_{AG} &\sim N(-2.2, 6.9).\end{aligned}$$

where $IG(\alpha, \beta)$ is the inverse gamma distribution defined by:

$$f(x|\alpha, \beta) = \frac{\beta^\alpha e^{-\beta/x}}{x^{\alpha+1}\Gamma(\alpha)}.$$

These choices of α and β correspond to a mean weight parameterization with mean 6.9 and weight 2. The prior for μ and θ_{AG} centers the response rate at 10% (the assumed underlying control rate).

Table 9 Design Characteristics for Bayesian Hierarchical Design for Part 2A DLBCL Cohorts

Scenarios for ORR	Proportion of MTAP- group meeting success criteria	Proportion of MTAP+ group meeting success criteria
0.3 in MTAP-; 0.3 in MTAP+	81.3%	81.7%
0.1 in MTAP-; 0.1 in MTAP+	8.3%	8.2%
0.3 in MTAP-; 0.1 in MTAP+	80.4%	10.3%

*The results are based on 5000 simulations with interim futility analysis starting after at least five participants in each subgroup and being done every 12 weeks.

Part 2B Solid Tumor Cohorts

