9.4.2. Dose Expansion Cohorts

9.4.2.1. Efficacy Analyses

Part 2A DLBCL Cohort

For Part 2A DLBCL cohort, the first interim analysis will be performed when at least 10 participants become evaluable in each of the MTAP defined subgroup. Data from both subgroups will be included in the analysis to form the Bayesian hierarchical model. For each MTAP defined subgroup, the therapeutic effect will be declared insufficient and enrolment will be terminated if the posterior probability of $ORR > 10\%$ is sufficiently low ($<20\%$) based on the hierarchical model. The interim futility analysis will be performed every 2-3 months depending on enrolment rate with minimum of additional five evaluable participants for the cohort. If only one subgroup is stopped early due to futility, the other subgroup will continue enrolment with the constraint of maximum of 30 participants for one subgroup and maximum of 36 participants for the entire cohort.

Part 2B Solid Tumor Cohorts

For Part 2B solid tumor cohorts, the first interim futility analysis will be performed when at least five participants become evaluable from MTAP proficient subgroup within any cohort. Data from all three cohorts will be included in the analysis to form the Bayesian hierarchical model.

For each MTAP+ subgroup within an individual expansion cohort, the therapeutic effect will be declared insufficient and enrolment will be terminated to MTAP+ participants if there are at least 5 MTAP+ participants within that cohort and the posterior probability of $ORR > 10\%$ is sufficiently low ($<20\%$) based on the hierarchical model. That is,

$$P(\pi_{j,MTAP+} > 10\% \mid \text{current data}) < 20\%, \text{ for the } j\text{-th cohort}$$

For each individual expansion cohort, the therapeutic effect will be declared insufficient and enrolment will be terminated to all participants (regardless of MTAP status) if at least 5 MTAP+ and 5 MTAP- participants within that cohort have ORR data and the posterior

probability that the ORR is greater than 10% is sufficiently low (<20%) based on the hierarchical model. That is,

$$P(\pi_{j,MTAP+} > 10\% \mid \text{current data}) < 20\%, \text{ for the } j\text{-th cohort AND}$$

$$P(\pi_{j,MTAP-} > 10\% \mid \text{current data}) < 20\%, \text{ for the } j\text{-th cohort}$$

The interim futility analysis will be performed every 2-3 months depending on enrolment with minimum additional five evaluable participants across all cohorts.

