All evaluable population will be used for the interim futility analyses. Within each design, the cohort/subgroup may be stopped early for futility but not for efficacy.

The final decision to close a cohort or the study based on futility will be made by the Sponsor, taking into consideration the results of the futility analyses and the entirety of the available data.

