## 4. ANALYSIS POPULATIONS

| Population           | Definition / Criteria  | Analyses Evaluated   |
|----------------------|--|--|
| Screened             | 
 
All participants who were screened for eligibility
 
   | 
 
Study Population
 
   |
| Evaluable            | 
 
All participants who have had Week 24 disease assessments, have progressed or died, or permanently discontinued from the study intervention.
 
 |  |
| All-Treated          | 
 
All participants who received at least one dose of GSK3368715.
 
   | 
 
Study Population
 
Final Efficacy
 
Safety
 
 |
| Pharmacokinetic (PK) | 
 
Participants in the All-Treated population from whom at least one PK sample was obtained, analysed, and was measurable.
 
                      | 
 
PK
 
   |

Refer to [Appendix 10](#): List of Data Displays which details the population used for each display.

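### Entry to the Part 2 futility population depends on outcome, so early looks under-count responders and lean towards stopping an active subgroup

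*Protocol*

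**What the plan says.** Protocol Section 9.3 admits to the All Evaluable population "Participants who have had Week 24 disease assessments, have progressed or died, or permanently discontinued from the study intervention". SAP Section 4 repeats the definition ("All participants who have had Week 24 disease assessments, have progressed or died, or permanently discontinued from the study intervention") but assigns no analysis to it. Protocol Section 9.4.2.1 states that "All evaluable population will be used for the interim futility analyses". Section 9.6.1 agrees, and bases the final efficacy analysis on the All-Treated Population.

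The rules fed by this population are:
- **Part 2A (Section 4.1.2):** "Any subgroup with posterior probability of ORR > 10% sufficiently low (<20%) will be declared as ineffective and terminated for enrollment". At the end of the study a subgroup counts as effective "if the posterior probability of ORR>10% is more than 85" per cent (Section 9.2.2).
- **Part 2B (Section 9.4.2.1):** at the same 20% cut, with at least 5 MTAP+ participants in the cohort, "the therapeutic effect will be declared insufficient and enrolment will be terminated to MTAP+ participants". A whole histology closes only if both MTAP subgroups cross.
- **Timing of the first look, Part 2A:** Section 4.1.2 says the "first interim futility analysis will be performed when at least 5 participants become evaluable from each of the MTAP defined subgroups". The Table 9 footnote and SAP Section 2.3 also use 5. Protocol Section 9.4.2.1 requires 10 per subgroup.
- **Timing of the first look, Part 2B:** five evaluable MTAP+ participants in any cohort.

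Section 8.1 schedules scans after 8 weeks and then 8-weekly to Week 32, with response confirmed at least 4 weeks later.

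**The concern.** A participant who progresses at the Week 8 scan joins the interim denominator at once. One whose response is seen at Week 8 and confirmed by Week 12 to 16 does not join until Week 24 while that response continues. Stable disease also waits, but confirmed response is the only outcome that counts in favour of the drug, and it has no early route in. Among participants dosed less than 24 weeks before a look, those counted are mostly failures.

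At stake is enrolment to a subgroup in which the drug works. Section 9.1.2 sets the standard: "All evaluations in Part 2 are designed to exclude a 10% response rate representing best available therapy in favour of a 30% response rate". Neither the Table 9 footnote nor the text around Table 10 says that outcome-dependent entry was simulated.

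**Working it through.** **Inputs from the protocol.** ORR 10% against 30%; futility if P(ORR>10%) < 20%; success if > 85%; at most 36 in Part 2A and 30 per subgroup; 50:50 MTAP split; looks every 12 weeks with at least 5 more evaluable participants. Prior: θ_g ~ N(μ, τ²), μ ~ N(−2.2, 6.9), τ² ~ IG(1, 47.61). Since 47.61 = 6.9², I read 6.9 as an SD; reading it as a variance gave the same fixed-sample decisions. The offset R_g is not defined. I set it to zero, because the prior is said to centre on 10% and ln(0.1/0.9) = −2.2.

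**Assumed, because the documents are silent.** Accrual of 0.25 to 1 per week to the whole cohort; 50% of non-responders progress at Week 8, 25% at Week 16 and the rest become evaluable at Week 24; responders remain on treatment to Week 24; looks fall on a 12-week calendar grid.

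**Step 1: reproduce Table 9.** With no interim look, success needs 4 of 18: P(X≥4) = 0.835 at 30% and 0.098 at 10%. With looks from 5 per subgroup, 0.75 per week and everyone evaluable at a fixed 24 weeks (5,000 runs):

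| True ORR (MTAP− / MTAP+) | Simulated success | Table 9 |
|---|---|---|
| 0.3 / 0.3 | 80.6% / 80.5% | 81.3% / 81.7% |
| 0.1 / 0.1 | 9.4% / 9.5% | 8.3% / 8.2% |
| 0.3 / 0.1 | 81.0% / 9.8% | 80.4% / 10.3% |

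Power agrees within 2 points. The null row differs by about 1 point.

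**Step 2: how sensitive the boundary is.** Under this prior, 0 of 5 gives P(ORR>10%) of about 0.03 to 0.07, which stops the subgroup. One of 5 gives about 0.62 to 0.66, which does not. One uncounted responder decides the matter. An unselected five at ORR 30% has no responder with probability 0.7⁵ = 16.8%.

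**Step 3: expected ORR at a look T weeks after first enrolment (T ≥ 24).** Per unit of accrual:
- dosed 8 to 16 weeks ago: 8 × 0.7 × 0.50 = 2.8 evaluable, none responding;
- dosed 16 to 24 weeks ago: 8 × 0.7 × 0.75 = 4.2 evaluable, none responding;
- dosed more than 24 weeks ago: T − 24 evaluable, 30% responding.

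Expected ORR is about 0.3(T − 24)/(T − 17). At 0.5 per week the expected number evaluable per subgroup is 0.25(T − 17): 4.75 at week 36 and 7.75 at week 48. The typical first look is therefore week 48, where ORR is 0.3 × 24/31 = 23%, not 30%.

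**Step 4: full-trial simulation.** True ORR 30% in both subgroups, first look at 5 per subgroup, 10,000 runs per row. The 24-week and 16-week rules count everyone first dosed at least that long ago.

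| Accrual per week | First-look ORR, as written | Stopped: as written / 24-week / 16-week | Power: as written / 24-week / 16-week |
|---|---|---|---|
| 0.25 | 26% | 14.6% / 10.3% / 10.3% | 76.0% / 78.6% / 78.8% |
| 0.5 | 23% | 16.6% / 8.0% / 8.4% | 74.3% / 79.8% / 79.8% |
| 0.75 | 20% | 17.1% / 4.9% / 6.3% | 73.1% / 80.8% / 80.6% |
| 1 | 17% | 14.5% / 1.8% / 4.0% | 73.5% / 82.1% / 81.5% |

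First-look ORR is 30% under both time rules. At 1 per week a look precedes full enrolment in 48%, 19% and 54% of runs respectively, so part of the gap to the 24-week rule reflects fewer looks. The 16-week rule has a similar look frequency and still shows 4.0% against 14.5%. It assumes every response is confirmed by 16 weeks.

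**Step 5: sensitivity.**
- With 30% to 70% of non-responders progressing at Week 8, stopping as written ranges from 6% to 26%, always above the time-based rules.
- With 20% of responders progressing at Week 16 (0.5 per week), first-look ORR is about 24% and stopping about 14%.
- With a first look at 10 per subgroup (0.5 per week), stopping is about 1.9% against 0.5% and power about 83% either way.

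Table 10 cannot be rebuilt, because the Part 2B priors are not stated.

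**The case against.** Several counter-arguments have force.

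- **The sponsor decides on all the data (Section 9.4.2.1).** True, and ongoing responders would be visible. But the posterior that informs the decision would still be biased.
- **The final ORR uses All-Treated.** True. The effect acts only through early closure.
- **The SAP cancels Part 2 and the futility looks (Sections 2.1 and 3.1.3).** True. No reported result changes.
- **Waiting for Week 24 gives responses time to mature.** That is a sound aim, but a 24-week rule applied to everyone meets it without selection.
- **The written rule also stops more inactive subgroups.** At 10% ORR and 0.5 per week, about 64% against 46%. That amounts to an undeclared tightening of the futility cut.

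Stronger readings are tempting. A reader might take the chance that the first five evaluable contain no responder as the chance of stopping. With an assumed non-responder median PFS of 10 weeks, it is 0.31, 0.51 and 0.84 at 1, 2 and 4 participants per month per subgroup. The documents do not support that reading: they state no accrual rate, and this chance is neither a stopping probability nor a loss of power. At 4 per month about 20 participants are already enrolled in the subgroup by then, and 71% of runs have reached the 18 expected at a 50:50 split, so little enrolment is left to stop.

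A reader might also infer that every responder waits for Week 24. Responders who progress, die or discontinue enter earlier, which shrinks the bias without removing it.

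**Conclusion.** The concern holds as a design flaw of moderate size. The direction follows from the definition itself. The size depends on assumed accrual and progression timing. With a first Part 2A look at 5 per subgroup, wrongful stopping is about 14.5% to 17.1% against 1.8% to 10.3%, and power falls by about 3 points (78.6 − 76.0 = 2.6) to 9 points (82.1 − 73.5 = 8.6). With a first look at 10 it is negligible, so which number governs decides whether Part 2A has a material problem.

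The Part 2A figures should not be carried over to Part 2B. Five MTAP+ participants is unambiguous there, but the priors are missing, the model borrows across cohorts and subgroups, and MTAP− closes only together with MTAP+. The point concerns the protocol as written and any reuse of the design, not the study's results.

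**What to change.** Define interim evaluability by time: all treated participants first dosed at least a fixed number of weeks before the data cut-off, whatever their status, with those lacking a confirmed response counted as non-responders. State the period and its reason:
- **20 to 24 weeks** covers the Week 16 scan plus 4 weeks for confirmation. With the 7-day scan window the sum is 16 + 1 + 4 = 21 weeks.
- **16 weeks** is acceptable if the plan says that only responses first seen at the Week 8 scan can be confirmed by then.

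Reconcile 5 with 10 for the first Part 2A look (Protocol Section 4.1.2, the Table 9 footnote and SAP Section 2.3 against Protocol Section 9.4.2.1). Then re-simulate Tables 9 and 10, stating the accrual rate, the time to evaluability and the Part 2B priors.

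The cost is one definition and a re-simulation. Under the Step 3 assumptions the number evaluable grows as T − 17 as written, against T − 24, T − 20 or T − 16. A 24-week rule therefore delays a given count by about 7 weeks, a 20-week rule by about 3, and a 16-week rule brings it forward by about 1. The longer cut-offs mean a later first look and, under fast accrual, fewer looks before enrolment is full. The shortest misses late responses at the look.

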9.4. Interim Analysis

9.4.1. Dose escalation and safety analyses

The primary driver for the dose-escalation decision(s) will be safety and tolerability of each dose cohort.

For Part 1 dose escalation and de-escalation decisions will be guided by an N-CRM model. Predicted DLT rates will be provided with the aim of escalating to doses with small probability of excessive or unacceptable toxicity.

Further details regarding such analyses will be provided in the Reporting and Analysis Plan (RAP).

9.4.2. Dose Expansion Cohorts

9.4.2.1. Efficacy Analyses

Part 2A DLBCL Cohort

For Part 2A DLBCL cohort, the first interim analysis will be performed when at least 10 participants become evaluable in each of the MTAP defined subgroup. Data from both subgroups will be included in the analysis to form the Bayesian hierarchical model. For each MTAP defined subgroup, the therapeutic effect will be declared insufficient and enrolment will be terminated if the posterior probability of $ORR > 10\%$ is sufficiently low ($<20\%$) based on the hierarchical model. The interim futility analysis will be performed every 2-3 months depending on enrolment rate with minimum of additional five evaluable participants for the cohort. If only one subgroup is stopped early due to futility, the other subgroup will continue enrolment with the constraint of maximum of 30 participants for one subgroup and maximum of 36 participants for the entire cohort.

Part 2B Solid Tumor Cohorts

For Part 2B solid tumor cohorts, the first interim futility analysis will be performed when at least five participants become evaluable from MTAP proficient subgroup within any cohort. Data from all three cohorts will be included in the analysis to form the Bayesian hierarchical model.

For each MTAP+ subgroup within an individual expansion cohort, the therapeutic effect will be declared insufficient and enrolment will be terminated to MTAP+ participants if there are at least 5 MTAP+ participants within that cohort and the posterior probability of $ORR > 10\%$ is sufficiently low ($<20\%$) based on the hierarchical model. That is,

$$P(\pi_{j,MTAP+} > 10\% \mid \text{current data}) < 20\%, \text{ for the } j\text{-th cohort}$$

For each individual expansion cohort, the therapeutic effect will be declared insufficient and enrolment will be terminated to all participants (regardless of MTAP status) if at least 5 MTAP+ and 5 MTAP- participants within that cohort have ORR data and the posterior

probability that the ORR is greater than 10% is sufficiently low (<20%) based on the hierarchical model. That is,

$$P(\pi_{j,MTAP+} > 10\% \mid \text{current data}) < 20\%, \text{ for the } j\text{-th cohort AND}$$

$$P(\pi_{j,MTAP-} > 10\% \mid \text{current data}) < 20\%, \text{ for the } j\text{-th cohort}$$

The interim futility analysis will be performed every 2-3 months depending on enrolment with minimum additional five evaluable participants across all cohorts.

All evaluable population will be used for the interim futility analyses. Within each design, the cohort/subgroup may be stopped early for futility but not for efficacy.

The final decision to close a cohort or the study based on futility will be made by the Sponsor, taking into consideration the results of the futility analyses and the entirety of the available data.

9.5. Final Analysis

The final analyses will be conducted when the study is completed. Data from the dose escalation and expansion cohort will be combined as appropriate.

9.6. Key Elements of Analysis Plan

Data will be listed and summarized according to the GSK reporting standards, where applicable. Complete details will be documented in the RAP. Any deviations from, or additions to, the original analysis plan described in this protocol will be documented in the RAP and clinical study report.

All data up to the time of study completion/withdrawal from study will be included in the analysis, regardless of duration of intervention and duration of follow-up.

Demographic and baseline characteristics will be summarized.

Unless otherwise specified, Part 1 will be summarized by dose, Part 2 will be summarized by disease type and MTAP status if applicable. Participants enrolled in Part 1 dose escalation and treated at expansion cohort dose will be included in the analysis for Part 2 provided that the participant has the same tumor type as the expansion cohort.

